2.2 Treatment Assignment

After the participant’s eligibility is established and informed consent has been obtained, the participant will be enrolled and a number will be assigned through an interactive voice response system (IVRS). Also, the IVRS will be used to manage enrollment of participant subgroups. Specific instructions and procedures for using IVRS will be provided to the investigational site in a separate document/ manual.

The investigator (or designee) will register the participant for enrollment by following the enrollment procedures established by BMS. The following information is required for enrollment:

- Date of informed consent
- Date of birth
- Gender at birth
- Confirmed RCC histology
- Confirmed presence or absence of brain metastases
- KPS

2.3 Blinding and Unblinding

This is an open-label study, blinding procedures are not applicable.

2.4 Protocol Amendments

Amendments	Date of Issue	Summary of Major Changes
01	24-Feb-2017	
 1. To align protocol with most recent program standards for nivolumab 2. To correct inconsistencies and minor grammatical errors 3. Added language to indicate that the number of participants to be included in each cohort would be approximate. 4. If the number of participants in Cohorts 3 and 4 cannot be reached, the number of participants enrolled in the clear-cell or non-clear cell cohorts may be increased.

3 OBJECTIVES

3.1 Primary Objective

The primary objectives of this study are:

1. To assess the incidence of high grade (CTCAE v4 Grade 3-4 and Grade 5) IMAEs in participants with advanced or metastatic RCC who are treated with combination therapy of nivolumab 6 mg/kg + ipilimumab 1 mg/kg every 8 weeks alternating with nivolumab 480 mg flat dose every 8 weeks, staggered every 4 weeks in Cohort 1,
2. To assess the incidence of high grade (CTCAE v4 Grade 3-4 and Grade 5) IMAEs in participants with advanced or metastatic RCC who are treated with combination nivolumab

(3 mg/kg) and ipilimumab (1 mg/kg) every 3 weeks for 4 doses, followed by maintenance nivolumab (480 mg every 4 weeks), in the select subgroups of mRCC participants (nccRCC, asymptomatic brains metastasis, or any histology with KPS 50-60% in Cohorts 2, 3, and 4).

3.2 Secondary Objective

The secondary objectives of this study are:

1. To characterize the outcome of all high grade (CTCAE v4 Grade 3-4 and Grade 5) IMAEs in participants with advanced or metastatic RCC who are treated with combination therapy in different cohorts,
2. To assess efficacy of nivolumab in combination with ipilimumab by measuring PFS 1 at time of initial progression, ORR, time to response (TTR), and duration of response (DOR), in all treated participants in different cohorts using RECIST 1.1.

[REDACTED]

4 ENDPOINTS

4.1 Primary Endpoint

The primary endpoint is the incidence of high grade (Grade 3-4 and Grade 5) IMAEs.

IMAEs are specific events (or groups of PTs describing specific events) that include pneumonitis, diarrhea/colitis, hepatitis, nephritis/renal dysfunction, rash, endocrine (adrenal insufficiency, hypothyroidism/thyroiditis, hyperthyroidism, diabetes mellitus, and hypophysitis), and other specific events, considered as potential immune-mediated events by investigator that meet the definition summarized below:

1. Those occurring within 100 days of the last dose
2. Regardless of causality
3. With no clear alternate etiology based on investigator assessment, or with an immune-mediated component
4. Treated with immune-modulating medication (Of note, adrenal insufficiency, hypothyroidism/thyroiditis, hyperthyroidism, diabetes mellitus, and hypophysitis are considered IMAEs regardless of immune-modulating medication use, since endocrine drug reactions are often managed without immune-modulating medication).

The followings are the list of IMAEs in this study: skin, endocrinopathy, gastrointestinal, hepatic, renal, pulmonary, and neurologic adverse events.

4.2 Secondary Endpoints

The secondary objective of the study will be assessed by measuring the following:

1. Characterization of outcome of all high grade (Grade 3-4 and Grade 5) IMAEs: Time to onset, time to resolution and percentage of subjects who received immune modulating medication will be analyzed for high grade (Grade 3-5) IMAEs of interest. Time to onset is calculated from first dosing date to the IMAE event onset date. Time to resolution is calculated from the IMAE onset date to IMAE end date. If an IMAE is ongoing at the time of analysis, the time to resolution will be censored at the last contact date. Management of high-grade (Grade 3-5) IMAEs will be characterized according to the following for all treated subjects:
 1. Percentage of participants who received immune modulating medication (or hormonal replacement therapy),
 2. Percentage of participants who received ≥ 40 mg prednisone equivalents,
 3. Total duration of all immune modulating medications given for the event.
2. PFS 1: PFS 1 is defined as the time from first dose to the date of the first documented PD as determined by the investigator (per RECIST 1.1 criteria or clinical) or death due to any cause whichever occur first. Subjects who die without a reported PD and without subsequent anti-cancer therapy will be considered to have progressed on the date of their death. Subjects who did not progress or die will be censored on the date of their last evaluable tumor assessment. Subjects who did not have any on-study tumor assessments and did not die will be censored on the date of first dose. Subjects who received any subsequent anti-cancer therapy without a prior reported progression will be censored at the

last evaluable tumor assessment prior to or on the date of initiation of the subsequent anti-cancer therapy.

Table 4.2-1: Censoring Scheme Used in Primary Analysis of PFS 1

Situation	Date of Progression or Censoring	Outcome
No baseline tumor assessments	First dose	Censored
No on study tumor assessments and no death	First dose	Censored
Progression documented between scheduled visits (per RECIST 1.1 criteria or clinical)	Date of the first documented tumor progression	Progressed
No progression, no death	Date of last tumor assessment with no documented progression	Censored
New anticancer treatment started without a prior reported progression	Date of last tumor assessment prior to or on the date of initiation of the subsequent anti-cancer therapy	Censored
Death without progression and without subsequent anti-cancer therapy	Date of death	Progressed

3. **ORR:** ORR is defined as the number of subjects with a best overall response (BOR) of CR or PR divided by the number of response evaluable subjects. BOR is defined as the best response designation, as determined by the investigator, recorded between the date of first dose and the date of objectively documented progression (per RECIST 1.1 or Clinical) or the date of subsequent therapy, whichever occurs first. For subjects without documented progression or subsequent therapy, all available response designations will contribute to the BOR determination. For subjects who continue treatment beyond progression, the BOR should be determined based on response designations recorded up to the time of the initial RECIST 1.1 defined PD or clinical progression, whichever occurs first.
4. **TTR:** TTR is defined as time from the date of first dose to first documented CR or PR. Cohort 1 subjects who do not have a CR or PR will be censored at the maximum time of response + 1 day. Subjects who do not have a CR or PR in combined cohort 2, 3 and 4 will be censored at the maximum time of response in combined cohort +1 day.
5. **DOR:** DOR will be computed for subjects who achieve PR or CR only. The DOR is defined as the time between the date of first confirmed response to the date of the first documented tumor progression (per RECIST 1.1), or death due to any cause, whichever occurs first. Subjects who neither progress nor die will be censored on the date of their last evaluable tumor assessment. Subjects who received any subsequent anti-cancer therapy on or after the

date of first confirmed response will be censored at the last evaluable tumor assessment prior to or on the date of initiation of the subsequent anti-cancer therapy.

[REDACTED]

[REDACTED]

[REDACTED]

[REDACTED]

[REDACTED]

[REDACTED]

[REDACTED]

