4 OBJECTIVES AND ENDPOINTS

Table 4-1: Objectives and Endpoints

Objectives	Endpoints

Primary
 
 To assess the incidence of high grade (CTCAE v4 Grade 3-4 and Grade 5) IMAEs in participants with advanced or metastatic RCC who are treated with combination therapy of nivolumab 6 mg/kg + ipilimumab 1 mg/kg every 8 weeks alternating with nivolumab 480 mg flat dose every 8 weeks, staggered every 4 weeks (Cohort 1) To assess the incidence of high grade (CTCAE v4 Grade 3-4 and Grade 5) IMAEs in participants with advanced or metastatic RCC who are treated with combination nivolumab (3 mg/kg) and ipilimumab (1 mg/kg) every 3 weeks for four doses, followed by maintenance nivolumab (480 mg every 4 weeks), in the select subgroups of mRCC participants (nccRCC, asymptomatic brains metastasis, or any histology with KPS 50-60% (Cohorts 2, 3, 4)) 	
 incidence of high grade (CTCAE v4 Grade 3-4 and Grade 5) IMAEs

Secondary
 
 To characterize the outcome of all high grade (CTCAE v4 Grade 3-4 and Grade 5) IMAEs in participants with advanced or metastatic RCC who are treated with combination therapy in different cohorts. To assess efficacy of nivolumab in combination with ipilimumab by measuring, progression-free survival (PFS 1 at time of initial progression; objective response rate (ORR), time to response (TTR), and duration of response (DOR), in all treated participants in different cohorts using RECIST 1.1. 	
 Characterization of outcome of all high grade (CTCAE v4 Grade 3-4 and Grade 5) IMAEs (eg, time to onset, time to resolution, percentage of patients who received immune modulating medication) PFS 1, ORR, TTR, DOR

Table 4-1: Objectives and Endpoints

Objectives	Endpoints

[REDACTED]
	
[REDACTED]

[REDACTED]
	
[REDACTED]

[REDACTED]
	
[REDACTED]

[REDACTED]
	
[REDACTED]

[REDACTED]
	
[REDACTED]

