9.2.1.1 Adverse Events of Special Interest – Immune-mediated AEs

Immune-mediated AEs (IMAEs) are specific events (or groups of PTs describing specific events) that include pneumonitis, diarrhea/colitis, hepatitis, nephritis/renal dysfunction, rash, endocrine (adrenal insufficiency, hypothyroidism/thyroiditis, hyperthyroidism, diabetes mellitus, and hypophysitis), and other specific events, considered as potential immune-mediated events by investigator, that meet the definition summarized below:

- those occurring within 100 days of the last dose
- regardless of causality
- with no clear alternate etiology based on investigator assessment, or with an immune-mediated component
- treated with immune-modulating medication (Of note, adrenal insufficiency, hypothyroidism/thyroiditis, hyperthyroidism, diabetes mellitus, and hypophysitis are considered IMAEs regardless of immune-modulating medication use, since endocrine drug reactions are often managed without immune-modulating medication).

[Table 9.2.1.1-1](#) below provides a summary of the IMAEs category and their respective preferred terms.

Table 9.2.1.1-1: Preferred Terms Included in Analysis of IMAEs to Support Warnings and Precautions

IMAE Category	PTs included under IMAE Category
Pneumonitis	Pneumonitis, interstitial lung disease
Diarrhea/Colitis	Diarrhea, colitis, enterocolitis
Hepatitis	Hepatotoxicity, hepatitis, hepatitis acute, autoimmune hepatitis, AST increased, ALT increased, bilirubin increased, ALP increased
Adrenal insufficiency	Adrenal insufficiency
Hypothyroidism/Thyroiditis	Hypothyroidism, thyroiditis Thyroiditis acute (collapsed with thyroiditis for frequency), Autoimmune thyroiditis (collapsed with thyroiditis for frequency)
Hyperthyroidism	Hyperthyroidism
Hypophysitis	Hypophysitis
Diabetes mellitus	Diabetes mellitus, diabetic ketoacidosis
Nephritis and renal dysfunction	Nephritis, nephritis allergic, tubulointerstitial nephritis, acute renal failure, renal failure, increased creatinine
Rash	Rash, rash maculopapular

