10.3.2 Safety Analyses

All safety analyses will be performed on the Treated Population.

Endpoint	Statistical Analysis Methods
Primary	
The incidence for high grade (Grade 3-4 and Grade 5) IMAEs. The IMAEs of interest are the following: skin, endocrinopathy, gastrointestinal, hepatic, renal, pulmonary, and neurologic adverse events.

Secondary	
Additional descriptive statistics of high grade (Grade 3-4 and Grade 5) IMAEs will include median values using the Kaplan-Meier (KM) product-limit method with 95% CI using Brookmeyer and Crowley method of time to onset and time to resolution, and will be presented for all treated participants. Time to onset is calculated from first dosing date to the event onset date. The IMAEs of interest are the following: skin, endocrinopathy, gastrointestinal, hepatic, renal, pulmonary, and neurological adverse events. If a participant never experienced the given AE, the participant will be censored at the last contact date. Time to resolution is calculated from the AE onset date to AE end date. If an AE is ongoing at the time of analysis, the time to resolution will be censored at the last contact date.

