5 SAMPLE SIZE AND POWER

The sample size of the study is mainly determined by the feasibility concern. The study plans to enroll 200 participants; approximately 100 in Cohort 1, 50 in Cohort 2, 25 in Cohort 3, and 25 in Cohort 4 (approximately 100 in Cohort 1 and 100 in Cohorts 2-4 combined). Enrollment in Cohort 1 for participants with a favorable risk score will be capped at 25% of the total population to be enrolled in that cohort.

In general, the combination of nivolumab and ipilimumab has higher rates in IMAE of high grade (Grade 3-4) than nivolumab monotherapy. Study CA209016 reports that both combination treatment arms have approximately 40-60% high grade IMAEs (34.0% in N3+I1 arm and 63.8% in N1+I3 arm); Study CA209012 (for NSCLC) reports approximately 35% high grade IMAEs in both combined therapy arms. Given these reported values, the precision of half width of 95% confidence interval (CI) of AE rates is between 9.3% and 9.8% for 100 participants and between 6.6% and 6.9% for 200 participants pooled together. These precisions are deemed as acceptable in evaluating the research hypotheses with respect to study cohorts in terms of AE rates in the range reported by previous studies.

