7.6.2 Secondary Analyses

7.6.2.1 Characterization of Outcome of High Grade Immune-Mediated Adverse Events

Time to onset and time to resolution will be analyzed for high grade (Grade 3-5) IMAEs of interest. The IMAEs of interest are the followings: skin, endocrinopathy, gastrointestinal, hepatic, renal, pulmonary, and neurological adverse events. Median values using the Kaplan-Meier (KM) product limit method with 95%CI using Brookmeyer and Crowley method will be presented for all treated subjects.

Analysis of endpoints related to management of high-grade (Grade 3-5) IMAEs will be conducted based on General Methods specified in [Section 7.1](#).

[Redacted]

[Redacted]

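### The Kaplan-Meier median time to onset of high-grade IMAEs is not expected to be reached for single organ categories, and the medication percentage is fixed for non-endocrine events if the IMAE criteria are applied

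*SAP*

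**What the plan says.** **Onset.** SAP 7.6.2.1 covers time to onset and time to resolution of high-grade IMAEs: "Median values using the Kaplan-Meier (KM) product limit method with 95%CI using Brookmeyer and Crowley method will be presented for all treated subjects". Protocol 10.3.2 likewise plans medians "of time to onset and time to resolution, and will be presented for all treated participants". SAP 7.1 has analyses done separately for each of the four cohorts. SAP Appendix 3 defines onset per category, censors subjects without the event at the maximum follow-up in their treatment group, and describes the resulting plot as a cumulative rate over time. For time to resolution, Appendix 3 limits the measure to subjects who had an event. It gives no such limit for onset.

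**Management.** Protocol Table 4-1 gives, as one example of an outcome measure, the "percentage of patients who received immune modulating medication". SAP 4.2 turns this into "Percentage of participants who received immune modulating medication (or hormonal replacement therapy" and adds the percentage given at least 40 mg prednisone equivalents and the total duration of medication. The lead-in reads "Management of high-grade (Grade 3-5) IMAEs will be characterized according to the following for all treated subjects".

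**Definition.** Criterion 4 of the IMAE definition in SAP 4.1 is "Treated with immune-modulating medication". The only exception is a list of endocrine conditions, which, in the words of protocol 9.2.1.1, "are considered IMAEs regardless of immune-modulating medication use, since endocrine drug reactions are often managed without immune-modulating medication".

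**Rates.** SAP 5 cites "34.0% in N3+I1 arm and 63.8% in N1+I3 arm" for high-grade IMAEs overall in an earlier study, described there as roughly 40-60%, and about 35% in a lung cancer study. It gives no rate per organ category and none for the Cohort 1 regimen.

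**The concern.** The outcome of high-grade IMAEs is the first secondary objective of a safety trial, and time to onset is one of its named measures. A clinician wants to know when these events usually appear in patients who get them. A median over all treated subjects answers a different question: by when has half of the cohort had the event? If fewer than half ever have it, the table shows no median and says nothing about timing among those affected.

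The medication row raises a separate issue. Outside the endocrine list, an event counts as an IMAE only if it was treated with immune-modulating medication. The share of those cases that received such medication is then settled by the case definition and cannot describe how events were managed.

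**Working it through.** **Inputs.** Cohort sizes 100, 50, 25 and 25 (SAP 5). Overall high-grade rates 34.0%, 35% and 63.8%, and the verbal range 40-60% (SAP 5). Category rates are not in the documents; I assume 5% to 25%.

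**The plan's own figure.** SAP 5 states 95% half-widths of 9.3-9.8% for 100 participants and 6.6-6.9% for 200. With 1.96 × √(p(1−p)/n): n = 100 gives 9.28% at p = 0.34 and 9.80% at p = 0.50; n = 200 gives 6.57% and 6.93%. These reproduce. The documents give no figure for the onset median.

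**Step 1: when the median exists.** Under Appendix 3 nobody is censored before the group's maximum follow-up, so the curve falls only to 1 minus the crude proportion with the event. The median exists if that proportion is at least one half: 50 of 100, 25 of 50 or 13 of 25. A curve that just touches 50% is counted as reached, which favours the plan. I take the treatment group to be the cohort.

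**Step 2: chance of reaching it.** P(X ≥ n/2, rounded up), with X binomial(n, p):

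| True rate p | n = 100 | n = 50 | n = 25 |
|---|---|---|---|
| 15% (assumed, category) | <0.001% | <0.001% | 0.002% |
| 20% (assumed, category) | <0.001% | <0.001% | 0.04% |
| 25% (assumed, category) | <0.001% | 0.01% | 0.34% |
| 34.0% (cited, pooled) | 0.07% | 1.4% | 4.8% |
| 35% (cited, pooled) | 0.15% | 2.1% | 6.0% |
| 40% (low end of verbal range) | 2.7% | 9.8% | 15.4% |
| 60% (high end of verbal range) | 98.3% | 94.3% | 84.6% |
| 63.8% (cited, pooled) | 99.8% | 98.4% | 92.2% |

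The category result holds across the whole assumed range. The pooled result depends on which cited rate applies.

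**Step 3: medication row.** SAP 7.6.1.1 names seven categories: skin, endocrine, gastrointestinal, hepatic, renal, pulmonary and neurologic. Six are non-endocrine. If criterion 4 is applied, every case in those six was treated, so the percentage among cases is 100%. If all treated subjects are the denominator instead, the row equals the incidence in those categories and repeats part of the primary result. Only endocrine cases can move it. The 40 mg prednisone row and the duration of medication are not fixed in this way.

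**Step 4: how much a cases-only median would rest on.** At assumed category rates of 10-15%, expected cases are 10 to 15 in a cohort of 100, 5 to 7.5 in 50, and 2.5 to 3.75 in 25. For n = 25, P(X ≤ 2) is 0.072 + 0.199 + 0.266 = 0.537 at 10%, and 0.017 + 0.076 + 0.161 = 0.254 at 15%.

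**The case against.** **The median may well be reached.** A reader might infer that it will almost never be reached at the rates the plan expects. The documents do not support that. At the cited 63.8%, or at the 60% end of the verbal range, a pooled median is usually reached. No rate is given for Cohort 1's regimen, and a pooled onset is not clearly planned, since Appendix 3 works by category. The claim stands for single categories, and for a pooled onset only at 34-35%. Protocol 10.3.2 censors event-free participants at last contact, which could bring a pooled curve to 50% with fewer than half affected; but the protocol leaves detailed analyses to the SAP, so the Appendix 3 rule is used here.

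**An unreached median is not an error.** True. The Appendix 3 cumulative-rate curve is sound and shows when events occur. What is missing is a number for those who had the event.

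**The 100% may not apply.** A reader might take the medication row to be empty without condition. SAP 7.6.1.1 identifies IMAEs by a sponsor query kept in a separate file, and Appendix 3 describes lists of preferred terms; neither mentions a medication filter. Appendix 3 also defines a resolution time for events of interest where such medication was started, which would add nothing for non-endocrine IMAEs if all were treated, although it may be meant for other event types. So the 100% is conditional. If the filter is not applied, the analysed events differ from the SAP 4.1 definition.

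**The phrase on all treated subjects may name only the analysis population.** It may; the denominator is not stated.

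**A cases-only summary may already be planned.** Text after SAP 7.6.2.1 is redacted and table details sit in a Data Presentation Plan that is not available. One may exist, so its absence cannot be asserted.

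**Conclusion.** The point holds in limited form and is one to consider. Under the Appendix 3 rule, the onset median over all treated subjects is not expected to be reached for single organ categories: at most a 0.34% chance in any cohort, on assumed category rates up to 25%. If a pooled onset is also tabulated, the chance at the cited 34-35% is 0.07-0.15%, 1.4-2.1% and 4.8-6.0% for cohorts of 100, 50 and 25, against 92-99.8% at the cited 63.8%.

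The medication percentage is 100% of non-endocrine cases only on the condition that criterion 4 is applied in the analysis set; its endocrine part is informative either way. It would be wrong to conclude that the secondary endpoint as a whole is uninformative: time to resolution, the prednisone row, medication duration and endocrine management all keep their value. The IMAE definition and the primary incidence are untouched.

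**What to change.** **SAP 7.6.2.1.** Report the median and range of time to onset among subjects with the event, labelled as cases only, next to the Appendix 3 cumulative-rate curve, which stays. Where a category has two or fewer cases, list the individual times.

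**SAP 4.2.** State that the denominator of the management percentages is subjects with the high-grade IMAE. Report the medication or hormone-replacement row separately for endocrine IMAEs, with a footnote that it is fixed by definition for the other categories.

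**Cost.** One onset table and one management table to re-program, and wording in two SAP sections. The cases-only median is conditional on having the event and must not be read as a population median. It is thin in the cohorts of 25: two or fewer cases in 54% to 25% of trials at assumed category rates of 10-15%. If the redacted text already holds such a summary, only the SAP 4.2 wording remains to be changed.

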7.1 General Methods

In general, unless expressly stated otherwise, all analyses will be performed by separated Cohort 1, Cohort 2, Cohort 3 and Cohort 4. Except where otherwise stated in this SAP, all analyses and summaries will be performed for all treated subjects. Analyses based on the combination of Cohorts 2-4 are considered not necessary for CSR as Cohort 4 has low KPS and tolerability may not be the same with other groups.

Unless otherwise noted, the bulleted titles in the following subsections describe tabulations of discrete variables, by the frequency and proportion of subjects falling into each category, by cohorts (with total). Percentages given in these tables will be rounded and, therefore, may not always sum to 100%. Continuous variables will be summarized by cohort (with total) using the mean, standard deviation, median, minimum and maximum values.

Time to event distribution (i.e. progression free survival, overall survival and duration of response) will be estimated using Kaplan Meier (KM) techniques. When appropriate, the median along with 95% CI will be provided using Brookmeyer and Crowley methodology (using log-log transformation for constructing the confidence intervals). Rates at fixed timepoints (e.g. PFS 1 at 6 months) will be derived from the Kaplan Meier estimate and corresponding confidence interval will be derived based on Greenwood formula for variance derivation and on log-log transformation applied on the survivor function $S(t)$.

The CA209 Core Safety DPP refers to several analyses that are to be performed on subjects with extended follow-up. For these summaries, AEs occurring from the time of the first dose of study therapy through 100 days after the last dose of study therapy will be summarized. Further general methods information for the safety analyses, including general methods for AEs and laboratory tests can be found in Section 7.1 of the IO core SAP.

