Duration of treatment will be presented using a Kaplan-Meier curve whereby the last dose date will be the event date for those subjects who are off study therapy. Median duration of treatment and associated 95% CI will be provided. Subjects who are still on study therapy will be censored on their last dose date.

A by-subject listing of dosing of study medication (record of study medication, infusion details, and dose changes) and a listing of drug assignment and dispensation will be also provided.

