Time-to resolution of AE (any grade) for a specific category is defined as the longest time from onset to complete resolution or improvement to the grade at baseline among all clustered select AEs in this category experienced by the subject. Events which worsened into grade 5 events (death) or have a resolution date equal to the date of death are considered unresolved. If a clustered AE is considered as unresolved, the resolution date will be censored to the last known date alive. Improvement to the grade at baseline implies that all different adverse events in the clustered adverse event should at least have improved to the corresponding (i.e. with same preferred term)

baseline grade. This measure is defined only for subjects who experienced at least one AE in the specific category.

The time-to resolution of AE (grade 3-5) for a specific category is defined similarly with an onset date corresponding to a grade 3-5 AE.

Time-to resolution of drug-related AE (any grade or grade 3-5) is defined similarly but restricted to drug-related AE.

The time-to resolution of AE (any grade or grade 3-5, drug-related or all) where immune modulating medication was initiated is defined similarly with the additional condition that the subject started an immune modulating medication during the longest AE resolution period.

Time-to resolution for a specific subcategory is defined similarly but restricted to event of this subcategory.

Table A3-1: Derivation of Clustered AE of Interest

Type of clustered AE of interest	Derivation
Any grade	Collapse any on-treatment AE from the same category
Drug-related of any grade	Collapse any on-treatment drug-related AE from the same category
Grade 3-5	Collapse any on-treatment AE from the same category. Resolution will be based on the onset date of the earliest grade 3-5 records (if no grade 3-5 record, clustered AE is excluded)
Drug-related of Grade 3-5	Collapse any on-treatment drug-related AE from the same category Resolution will be based on the onset date of the earliest grade 3-5 record (if no Grade 3-5 record, clustered AE is excluded)

The algorithm for collapsing adverse event of interest (IMAE, select AE, other event of special interest) records uses the following conventions:

For each subject and specified category, the corresponding adverse event records will be collapsed when:

- 1) Multiple adverse event records have the same onset date.

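### Total duration of immune-modulating medication for high-grade IMAEs has no visible rule for courses still open, so a plain mean, and usually a plain median, would be too short if any are open

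*SAP*

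**What the plan says.** SAP 4.2, item 1, names three measures for the management of high-grade IMAEs: two percentages and "Total duration of all immune modulating medications given for the event". It does not say when the duration starts and stops, how gaps or overlapping drugs are counted, or what happens to a course that has not ended.

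SAP 7.6.2.1 gives Kaplan-Meier (KM) medians to time to onset and time to resolution. A separate sentence covers the management measures: "Analysis of endpoints related to management of high-grade (Grade 3-5) IMAEs will be conducted based on General Methods", with a pointer to Section 7.1.

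Section 7.1 contains two candidate methods. One is "Continuous variables will be summarized by cohort (with total) using the mean, standard deviation, median, minimum and maximum values". The other is "Time to event distribution (i.e. progression free survival, overall survival and duration of response) will be estimated using Kaplan Meier (KM) techniques". Medication duration is not in the second list.

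Two similar quantities do have a rule for open records. For time to resolution, SAP 4.2 says "If an IMAE is ongoing at the time of analysis, the time to resolution will be censored at the last contact date". For duration of study treatment, which SAP 7.4.1 presents as a KM curve, it says "Subjects who are still on study therapy will be censored on their last dose date".

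**The concern.** A course of medication that is still running has no observed length, only a lower bound. A mean or SD needs a single number for each participant. Without a censoring rule, the programmer can enter the length so far as if it were final, or leave the participant out. The first replaces a value by something smaller. The second tends to remove long courses, because a long course is more likely to be open at any given cut-off.

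At stake is the reported medication burden of high-grade IMAEs, which a reader of the study report would take at face value. The results are shown by cohort, so cohorts with different shares of open courses could show different durations for that reason alone.

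**Working it through.** The plan gives no figure for medication duration, so there is none to reproduce. The check covers the routing, whether open courses are foreseeable, and the direction and size of the effect.

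**1. Routing in the SAP**

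| Quantity | Method stated | Rule for open records |
|---|---|---|
| Time to resolution (4.2, 7.6.2.1) | KM median, 95% CI | Censored at last contact |
| Duration of study treatment (7.4.1) | KM curve, median, 95% CI | Censored at last dose |
| Duration of immune-modulating medication (4.2, 7.6.2.1) | General Methods, 7.1 | None visible |

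**2. Can courses be open?** Yes.

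- SAP 4.1 counts IMAEs with onset up to 100 days after the last dose.
- Protocol Table 2-5 marks concomitant-medication review for follow-up visits 1 and 2 only. Visit 2 is at about 100 days (±7) after the last dose. An IMAE starting on day 80, for example, leaves 100 − 80 = 20 days of scheduled medication review.
- Protocol 8.1.1 allows for prolonged steroid tapers.
- Protocol 10.3.5 places the final analysis when all participants have completed study treatment, and allows earlier data cuts for publication.

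**3. Direction and size, closed form.** Let the true course length T be exponential with mean μ. Let the end of observation C be exponential and independent of T. Let c = P(C < T) be the share of courses open.

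- Counted as complete: the recorded value is min(T, C), with mean μ(1 − c) and median equal to the true median times (1 − c).
- Dropped: T given T ≤ C has the same distribution as min(T, C), so the factor is the same.

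At c = 5%, 10%, 20% and 30%, mean and median are therefore low by 5%, 10%, 20% and 30%. At c = 0 there is no bias.

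**4. Size with a skewed distribution.** Course length is assumed lognormal with log-SD 1 and median 60 days. Censoring is independent and exponential, scaled to give each open share (400,000 simulated courses). The simulated truth is mean 98.9 and median 60.1 days.

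| Open share | Mean, counted complete | Mean, dropped | Median, counted complete | Median, dropped | KM median |
|---|---|---|---|---|---|
| 5% | 92.5 (−6%) | 91.3 (−8%) | 57.8 (−4%) | 57.6 (−4%) | 60.1 |
| 10% | 86.6 (−12%) | 85.0 (−14%) | 55.4 (−8%) | 55.2 (−8%) | 60.1 |
| 20% | 75.6 (−24%) | 74.0 (−25%) | 50.2 (−16%) | 50.4 (−16%) | 60.0 |
| 30% | 65.6 (−34%) | 64.8 (−34%) | 45.0 (−25%) | 45.9 (−24%) | 60.1 |

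True medians of 30 and 120 days give the same percentages to within about one point. Distribution, median and open shares are all assumptions; the documents supply none of them.

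**5. Numbers affected.** SAP Section 5 cites high-grade IMAE rates of 34.0% and 63.8% from an earlier study. Applied to the planned cohort sizes:

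- Cohort 1: 0.340 × 100 = 34 to 0.638 × 100 = 64
- Cohort 2: 0.340 × 50 = 17 to 0.638 × 50 = 32
- Cohorts 3 and 4, each: 0.340 × 25 = 8.5 to 0.638 × 25 = 16

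In Cohort 3 or 4, one open course is thus between 1/16 = 6% and 1/9 = 11% of the records, if all these participants received medication.

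**The case against.** **The rule may exist elsewhere.** The SAP defers general safety methods and conventions to an IO Core SAP that was not supplied, and text following 7.6.2.1 is redacted. This stands as a limit: the point concerns the visible text. A convention that only assigned an end date to open records would still leave a mean and SD of cut or imputed values, not a censored summary.

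**Section 7.1 also contains KM.** Its list is not complete in practice, since time to response, time to onset, time to resolution and duration of treatment are all analysed by KM and are absent from it. But each of those has its own explicit statement. Medication duration has none, so descriptive statistics remain the natural reading, though not the only possible one.

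**Open courses may be few.** The final analysis follows the end of study treatment, and Protocol Table 2-5 follows ongoing drug-related events until they resolve. This stands: the bias could be small.

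**A total with gaps is not a pure time-to-event variable.** Also true. Days summed over several drugs can be informatively censored, so the quantity must be defined before KM is applied.

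A reader might go further in three directions that the documents do not support.

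- *Deaths.* One might infer that courses ended by death are also understated, most of all in Cohort 4. Yet the measure is of medication given, and a course that ends at death has a known, complete length. The rule in SAP Appendix 3, "Events which worsened into grade 5 events (death) or have a resolution date equal to the date of death are considered unresolved", concerns resolution of the event, which is a different quantity.
- *Endocrine events.* One might infer that lifelong hormone replacement dominates the figure, so that it mostly measures follow-up. But the first management measure in SAP 4.2 names hormonal replacement alongside immune-modulating medication, and the duration measure does not. On its face the duration leaves it out.
- *The median.* It need not fall. If open courses are kept at their observed length and all were cut beyond the true median, the plain median is unchanged with up to half of the courses open.

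**Conclusion.** The point holds in a limited form and is minor. On the natural reading, the SAP summarises this duration as an ordinary continuous variable and gives no visible rule for open courses, although it censors two comparable durations. If any courses are open, counting them as complete lowers the mean with certainty. Dropping them lowers it under independent censoring. The median usually falls too.

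The size cannot be derived from the documents. Under the assumptions above, 10% open gives a mean about 10-14% low and a median about 8-10% low, and the bias vanishes if all courses have ended. These figures illustrate the mechanism and do not predict this trial's result. Nor do they support a claim that the cohorts cannot be compared: the visible SAP plans no formal comparison of this measure, which is one descriptive sub-item of a secondary endpoint.

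**What to change.** In SAP 4.2 and 7.6.2.1:

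- Define the duration as the time from first start to final stop of immune-modulating medication for the event, in participants with a high-grade IMAE who received such medication. This counts gaps as part of the course. If days actually on medication are also wanted, report them under a separate label.
- Summarise it by KM with the median and 95% CI, as is already done for duration of study treatment.
- Censor ongoing courses at the last date on which medication status is known, which may be earlier than last contact.
- Count death on medication as the end of medication given.
- Report the numbers of courses completed, ongoing and ended by death.
- State whether hormone replacement counts. If it does, show endocrine events separately.
- Confirm whether medication stop dates are collected after follow-up visit 2. If they are not, the censoring date above already covers it.

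The cost is a few sentences and one extra table, using data already collected. KM relies on independent censoring, and the medians in Cohorts 3 and 4 will be imprecise, with about 9-16 participants each at the cited rates.
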